Researchers will collect the following items and record them in the CRF: Symptoms of hypoglycemia; duration (start and end date and time); severity grading (Grade 1 hypoglycemia: blood glucose < 3.9 mmol/L and ≥ 3.0 mmol/L; Grade 2 hypoglycemia: blood glucose < 3.0 mmol/L; Grade 3 hypoglycemia: severe event requiring assistance from others for treatment, accompanied by altered consciousness and/or physical changes, but without specific blood glucose thresholds); Measures taken (self-feeding, assistance required to eat, assistance required to go to the hospital for intravenous glucose infusion; other); Outcome; Blood glucose level measured by a blood glucose meter (at the time of hypoglycemia); Time of blood glucose measurement by a blood glucose meter (at the time of hypoglycemia);

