3.3.3 Visit 3A - Follow-up Period (Baseline \pm 3 days)

3.3.3.1 Patients in Group B undergo a physical examination (measurements: weight, waist circumference, blood pressure, pulse rate); blood samples are collected and frozen for storage (to be used for GA measurement at the end of the study); all data are recorded (medication changes, occurrence of hypoglycemia, other safety events). The study physician determines whether patients require medication adjustments based on clinical

guidelines (refer to Figure 2).

3.3.3.2 Patients in Group A undergo blood collection and GA measurement.

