3.3.4 Visit 3B - Follow-up Period (Visit 3A + 5 days)

- *Preferably within 3 days after Visit 3A, with a maximum of 5 days.
 - 3.3.4.1 Patients in Group B will not participate in this follow-up visit.
 - 3.3.4.2 Patients in Group A will undergo a physical examination (measurements: weight, waist circumference, blood pressure, pulse rate). The GA results for Group A patients will be communicated to the study physician and the patients. The study physician will adjust the medication based on the GA results.

Drug adjustments follow the "GA normalization" principle: if GA > 16%, the study physician increases the type of oral medication based on the 2020 Chinese Diabetes Prevention and Control Guidelines (Figure 2). Due to the risk of hypoglycemia, sulfonylureas, glinides, insulin, or insulin analogues are prohibited in this study. If $GA \le 16\%$, no drug adjustments are made. However, if a patient reports hypoglycemia within the past month, the cause of hypoglycemia must be identified first and appropriate management provided. Since this study excludes sulfonylureas, glinides, insulin, or insulin analogues, the theoretical risk of hypoglycemia is extremely low. If unexplained hypoglycemia occurs, the investigator may consider reducing the dose of oral hypoglycemic agents as appropriate.

3.3.4.3 Record all data (medication status, occurrence of hypoglycemia, and other adverse events).

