3.2 Study Procedures and Follow-up Schedule

The research steps and follow-up plan are shown in Figure 1 and Table 1.

[figure not shown]

Figure 1. Research process diagram

Table 1 Research flowchart

	Screening visits	Baseline [#]	Follow-up				Measurement of GA Frozen sample
Visit number	1	2	3A	3B	4	5	
visit time	Days -7 to 0	Day 0	4 weeks (baseline: 28 ± 3 days)	4 weeks (follow-up visit 3A + 5 days) [*]	8 weeks (baseline 56 \pm 3 days)	12 weeks (baseline 84 \pm 3 days)	Follow-up visit completed
informed consent	X						
Demographic information (name,	X						

gender, ethnicity, date of birth)							
Medical history ^a	X						
Physical examination ^b	X		X ^h	X ^g	X	X	
Collect samples and perform the following laboratory tests:							
Blood glucose-related tests ^c	X ⁱ					X	
Complete blood count ^d	X ⁱ					X	
Liver and kidney function ^e	X ⁱ					X	
lipids ^f	X ⁱ					X	
Blood or urine pregnancy test	X ⁱ						
Blood sample collection (for GA measurement)	X		X ^h		X		
Inclusion/exclusion criteria	X	X					
Confirm eligibility for enrollment		X					
Randomization		X					
Treatment plan		X					
Distribution of subject diaries		X	X ^h	X ^g	X		
Check and collect participants' report			X ^h	X ^g	X	X	
GA measurement			X ^g			X	
Adjust treatment plan			X ^h	X ^g	X		
Recording medication treatment	X	X	X ^h	X ^g	X	X	
Record and review		X	X ^h	X ^g	X	X	

(since the previous visit)						
(S) AE						
study termination					X	
Determination of GA in frozen samples						X

Notes:

- #If screening and baseline are conducted on the same day, all duplicate steps need only be performed once
- *It is best to conduct the visit within 3 days after the 3A visit, with a maximum of 5 days
- a. Medical history includes information such as disease course and treatment methods
- b. Physical examination includes: height, weight, waist circumference, blood pressure, pulse (screening period); weight, waist circumference, blood pressure, pulse (follow-up period)
- c. Blood glucose-related tests include: fasting blood glucose, HbA1c, fasting C-peptide, fasting insulin
- d. Complete blood count: red blood cells (RBC), white blood cells (WBC), platelets (PLT), hemoglobin (HGB)
- e. Liver and kidney function: total bilirubin (Tbil), alanine transaminase (ALT), aspartate transaminase (AST), total protein (TP), albumin, blood urea nitrogen (BUN) or urea (Urea), serum creatinine (Cr), uric acid (UA)

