4.2. Safety indicators

4.2.1. Exposure time: Not applicable.

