*** Hypoglycemia Incidence and Frequency:**

Calculate the number of episodes, total number of episodes, and percentage of participants in the intervention group and control group who experienced hypoglycemia during each visit (V3A—control group visit/V3B—intervention group visit, V4). For hypoglycemia incidence rates, use chi-square tests or Fisher's exact probability test for between-group comparisons.

List the hypoglycemia episodes experienced by participants at each visit.

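### The SAP's by-visit hypoglycemia comparison uses slightly unequal windows (3A for control, 3B for intervention) and does not list Visit 5, which leaves out a third of follow-up

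*SAP*

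**What the plan says.** The hypoglycemia entry in SAP 7.4.2 asks for episode counts and the percentage of participants "who experienced hypoglycemia during each visit (V3A—control group visit/V3B—intervention group visit, V4". It continues: "For hypoglycemia incidence rates, use chi-square tests or Fisher's exact probability test for between-group comparisons". The entry gives no person-time denominator, no rule for assigning an episode to a visit, and no mention of Visit 5. Under safety, the SAP has "4.2.1. Exposure time: Not applicable", and 7.5.1 repeats it.

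The schedule tables in both documents place Visit 3A at day 28 ± 3, Visit 4 at day 56 ± 3 and Visit 5 at day 84 ± 3, all counted from baseline. The arms differ at week 4:

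- Group B has its hypoglycemia recording and medication decision at Visit 3A (Protocol 3.3.3.1).
- For Visit 3A, Protocol 3.3.3.2 says only: "Patients in Group A undergo blood collection and GA measurement". Group A's hypoglycemia recording and medication decision come at Visit 3B, which Group B does not attend (Protocol 3.3.4). Its timing is "Preferably within 3 days after Visit 3A, with a maximum of 5 days".

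The schedule marks collection of participant reports and adverse event review at Visit 5 for both arms. SAP 4.1.2 describes all secondary endpoints as evaluated to Visit 5. SAP 7.7 lists two changes to the planned analyses, and neither limits hypoglycemia to Visit 4.

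The CRF items in Protocol 3.3.2.5 include "Symptoms of hypoglycemia; duration (start and end date and time".

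**The concern.** Incidence and frequency of hypoglycemia is a named secondary endpoint. The delay to Visit 3B applies only to Group A and only in one direction, unlike the ±3-day tolerances, which apply to both arms. Because Visit 4 is counted from baseline, each day added to Group A's interval before the treatment decision is taken from its interval after it. With equal true risk, the by-visit percentages would then differ: slightly high for Group A before the decision, slightly low after it.

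The second feature is the missing Visit 5. Treatment may be changed at week 4, so any effect of the GA-guided strategy on hypoglycemia would arise between then and week 12. As worded, the tested comparison stops at week 8. The shortened interval to Visit 4 then becomes the only listed comparison after the decision.

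**Working it through.** The documents state no hypoglycemia rate or power, so there is no figure of theirs to reproduce.

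**Inputs.** Nominal visit days 28 (3A), 56 (V4) and 84 (V5) come from the schedule tables. The gap g from 3A to 3B is at most 5 days, preferably no more than 3 (Protocol 3.3.4). There are 100 participants per arm (SAP 3.3), and tests are two-sided at 0.05 (SAP 7.1). The 28-day incidence p is assumed.

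**Step 1: window lengths.** Group A's interval before the decision is 28 + g days, and the interval from there to Visit 4 is 56 − (28 + g) = 28 − g days. Group B has 28 days in each.

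- g = 3: 31 vs 28 days (31/28 = 1.107, +10.7%), then 25 vs 28 (25/28 = 0.893, −10.7%).
- g = 5: 33 vs 28 days (33/28 = 1.179, +17.9%), then 23 vs 28 (23/28 = 0.821, −17.9%).
- Baseline to Visit 4: 56 ± 3 days in both arms, so no systematic difference.

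**Step 2: effect on the percentages.** With the same constant hazard in both arms, Group A's expected incidence is 1 − (1 − p)^((28 + g)/28) before the decision and 1 − (1 − p)^((28 − g)/28) after it. For example, with p = 10% and g = 5: 1 − 0.90^(33/28) = 11.68% and 1 − 0.90^(23/28) = 8.29%.

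| Assumed 28-day incidence | A minus B, g = 3 (before / after) | A minus B, g = 5 (before / after) |
|---|---|---|
| 1% | +0.11 / −0.11 points | +0.18 / −0.18 points |
| 2% | +0.21 / −0.21 | +0.35 / −0.35 |
| 5% | +0.52 / −0.52 | +0.87 / −0.87 |
| 10% | +1.01 / −1.02 | +1.68 / −1.71 |

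**Step 3: effect on the test.** This is the exact rejection probability of the uncorrected chi-square test with 100 per arm, equal true hazard and g = 5. At p = 5% it is 4.4% with equal windows, against 5.2% (before) and 5.1% (after). At p = 10% it is 5.2%, against 6.8% and 7.2%.

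**Step 4: expected episode counts.** At a constant rate these scale with days, so their relative distortion is 11-18% whatever the rate. The SAP names a test only for incidence, not for counts.

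**Step 5: time not listed.** Visit 4 to Visit 5 is 84 − 56 = 28 days, or 28/84 = 33% of follow-up. As a share of time after the week-4 decision it is 28/56 = 50% in Group B. In Group A it is 28/53 = 53% (g = 3) or 28/51 = 55% (g = 5).

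**The case against.** The strongest defence is that the pairing of 3A with 3B is deliberate and sensible. Each interval ends at that arm's own treatment decision, so none mixes time before and after it. That stands. It justifies the boundaries, but not comparing raw percentages over intervals of different length.

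The size is also fairly disputed. Five days is the ceiling. Protocol 3.3.4 calls the theoretical hypoglycemia risk extremely low, because sulfonylureas, glinides and insulin are prohibited. At 1-2% per 28 days the shift is under half a participant per 100. This stands too: at such rates the window effect is negligible.

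A reader might infer that the analysis favours the GA arm overall, or that nothing in the plan deals with the difference. The documents support neither. The two interval shifts are nearly equal and opposite, and the baseline-to-Visit 4 total is balanced. SAP 7.2.3 (special data notes) appears in the table of contents, but its text was not available, and the programming specifications are a separate file. A rule for assigning episodes could be in either. The exposure-time entry sits under safety, while hypoglycemia is an efficacy secondary endpoint, so it is weak evidence of how this endpoint will be handled.

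Episodes after Visit 4 may also appear in the adverse event summaries of SAP 7.5.2, which are not split at these visits. Those summaries are descriptive, so they do not restore the missing period to the tested comparison.

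**Conclusion.** The point holds as a minor one. The by-visit comparison in SAP 7.4.2 uses windows that differ systematically by up to 5 days, in opposite directions before and after the week-4 decision, with no person-time adjustment in the available text. The bias stays below 1 percentage point at a 28-day incidence of 5% or less, and is about 1.7 points at 10% with the full 5-day gap. These figures rest on assumed rates, an equal constant hazard and nominal visit days. The primary endpoint is unaffected.

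The more consequential feature of the same sentence is that Visit 5 is not listed. That leaves a third of nominal follow-up, and at least half of the time after the treatment decision, outside the stated comparison, although the schedule has diaries and adverse events reviewed at Visit 5. It may be a drafting slip. If so, it is easily corrected.

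**What to change.** In SAP 7.4.2:

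1. Assign each episode by its recorded start date, not by the visit at which it was reported.
2. Make the between-group comparison the cumulative incidence and the episodes per patient-day from randomisation to Visit 5, with actual visit dates (or last contact after early withdrawal) setting the denominator. Name a method for the rate that allows for repeated episodes in one participant.
3. Report the period from each arm's week-4 treatment decision (3A for Group B, 3B for Group A) to Visit 5 as a rate per patient-day.
4. Keep the 3A/3B and Visit 4 counts as description only.

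If SAP 7.2.3 or the programming specifications already hold an assignment rule, a cross-reference would cover item 1.

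The cost is SAP wording and a small programming change. No new data should be needed, because Protocol version 2.0 has the CRF record episode start and end times. The SAP is based on Protocol version 3.0 and CRF version 3.0, so confirm first that the later CRF still records these dates.

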*** Changes in pancreatic β -cell function**

*** Changes in insulin resistance levels**

*** Body weight**

*** Waist circumference**

*** Changes in BMI**

For the above secondary efficacy endpoints, calculate the change values and percentage changes relative to the screening period at the end of treatment (V5). For continuous variables, use t-tests or Wilcoxon rank-sum tests for between-group comparisons.

Among these, Percentage change relative to the screening period at the end of treatment (V5) = (indicator results at visit 5 - indicator results at the screening period)/ indicator results at the screening period

The indicator results are the results of the above secondary efficacy endpoints.

7.5 Safety Analysis

7.5.1 Exposure Time: Not applicable.

7.5.2 Adverse Events (AEs)

Coding: All AEs will be coded using MedDRA/C [v27.0].

Summarize the number of cases, incidence rates, and frequency of adverse events, serious adverse events, adverse events related to drug therapy, serious adverse events related to drug therapy, and adverse events leading to withdrawal from the study that occurred during the research process.

Summarize adverse events, serious adverse events, adverse events related to drug therapy, serious adverse events related to drug therapy, and adverse events leading to withdrawal from the study according to SOC/PT and describe them in groups. If the same patient experiences multiple adverse events, count it as one case when calculating the incidence rate; if a patient experiences the same AE multiple times, count it as one case in the AE incidence rate calculation.

Severity of adverse events: Assess the severity of AEs as mild, moderate, or severe, and summarize the number of cases, incidence rate, and severity of adverse events for each severity level. If a subject experiences multiple AEs, the most severe AE is included in the analysis of the number of adverse events; if a subject experiences the same AE multiple times, the most severe occurrence is included in the analysis of the incidence rate for that severity level.

Adverse events related to drug therapy: Adverse events classified as “definitely related,” “likely related,” or “possibly related” to drug therapy.

Provide a summary table of adverse events by subcenter.

Provide a list of all types of adverse events.

7.5.3 Device Defects: Not applicable.

7.5.4 Laboratory Test Results

Conduct a statistical description of the quantitative results of laboratory tests (glucose-related tests, complete blood count, liver and kidney function, lipid profile) for screening visits and visit 5, as well as any changes from the screening

period. Classify pre-treatment and post-treatment laboratory test results into the following categories: clinically significant abnormalities, non-clinically significant abnormalities, normal, and not tested, in that order. Then generate a conversion table.

List all laboratory test results.

7.5.5 Electrocardiogram (ECG): Not applicable.

7.5.6 Other Safety Assessments

***Physical examination**

Descriptive statistics were performed on the height of participants during the screening period. For the remaining indicators, namely systolic blood pressure, diastolic blood pressure, and pulse rate, descriptive statistics were performed on the data from each visit. Since descriptive statistical analysis of weight, waist circumference, and BMI had already been conducted in the secondary endpoint indicators, no summary is provided here. A list of physical examination items for participants is provided.

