3.3.5 Visit 4 – Follow-up period (baseline ± 3 days)

- 3.3.5.1 Physical examination (measurements: weight, waist circumference, blood pressure, pulse rate);
- 3.3.5.2 Blood samples collected and frozen for storage in both Group A and Group B (to be measured for GA at the end of the study);
- 3.3.5.3 Record all data (medication changes, occurrence of hypoglycemia, other safety events).
- 3.3.5.4 The study physician conducting this visit should generally not adjust medications. However, adjustments may be made if the patient reports adverse events related to medication. Since this study excludes sulfonylureas, glinides, insulin, and insulin analogues, the theoretical risk of hypoglycemia is extremely low. If the patient reports hypoglycemia within the past month, the cause must first be identified and appropriate management provided. If unexplained hypoglycemia occurs, the investigator may consider reducing the dose of oral hypoglycemic agents as appropriate.

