4.1.2. Secondary Endpoints

Secondary endpoints include:

- Proportion of subjects with HbA1c < 6.5% at Visit 5
- Proportion of subjects with HbA1c < 6.0% at Visit 5
- Change in HbA1c from screening to Visit 5
- Incidence and frequency of hypoglycemia
- Change in pancreatic β-cell function
- Change in insulin resistance
- Change in body weight
- Change in waist circumference
- Change in BMI

All secondary endpoints will be evaluated as changes from screening to the end of treatment (Visit 5), including absolute and percentage changes.

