7.2. Data processing methods

7.2.1. Advance withdrawl and missing data

All missing data will not be imputed.

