7.4.2 Secondary Endpoint Analysis

Analysis will be conducted using both FAS and PPS.

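### SAP 7.5.6 omits by-visit summaries of weight, waist and BMI as already covered, but the secondary analysis covers only the screening-to-Visit 5 change, so week-4 and week-8 values are listed and not analysed

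*SAP*

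**What the plan says.** In SAP 7.5.6 (Physical examination), blood pressure and pulse are treated visit by visit: "descriptive statistics were performed on the data from each visit". Weight, waist and BMI are left out of that treatment: "Since descriptive statistical analysis of weight, waist circumference, and BMI had already been conducted in the secondary endpoint indicators, no summary is provided here". The only other output in the section is a listing: "A list of physical examination items for participants is provided".

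The secondary-endpoint text pointed to is narrower. SAP 4.1.2 fixes the time point: "All secondary endpoints will be evaluated as changes from screening to the end of treatment (Visit 5), including absolute and percentage changes". For these three variables SAP 7.4.2 says to "calculate the change values and percentage changes relative to the screening period at the end of treatment (V5", with a t-test or Wilcoxon rank-sum test between groups. On the analysis sets it says: "Analysis will be conducted using both FAS and PPS". SAP 7.7 repeats the Visit 5 time point when it adds the percentage change.

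Measurement is more frequent than that. Protocol 3.3.3.1 has weight and waist taken at week 4 in Group B (Visit 3A), and 3.3.4.2 has them taken in Group A (Visit 3B). Protocol 3.3.5.1 requires them at week 8 in both groups: "Physical examination (measurements: weight, waist circumference, blood pressure, pulse rate". Table 1 of the SAP shows the same schedule. Height is taken at screening only, so BMI at follow-up has to be derived.

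On missing data, SAP 7.2.1 says: "All missing data will not be imputed".

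**The concern.** The reason given for leaving out the by-visit summary holds for Visit 5 and for no other follow-up visit. A reader of 7.5.6 would expect to find the course of weight, waist and BMI under the secondary endpoints, and it is not there. This also fits poorly with SAP 7.1, which requires all collected efficacy and safety data to enter the statistical analysis.

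Two consequences follow. First, weight, waist and BMI receive no summary on the safety set. Second, neither document schedules an early-termination measurement, so a subject who leaves before Visit 5 has no change value and falls out of three named secondary comparisons, even if weighed at weeks 4 and 8. For someone lost after week 8, the Visit 4 value is the only scheduled one taken after the GA-guided adjustment, and the planned tests do not use it. If leaving early is related to earlier weight, a comparison of completers could be biased in a way that data already in the database would help to reduce.

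**Working it through.** **1. What is measured against what is analysed (weight and waist; BMI derived)**

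| Time | Measured | Summarised or tested | Listed |
|---|---|---|---|
| Screening | both groups | as the reference for change | yes |
| Week 4 (3A Group B, 3B Group A) | yes | no | yes |
| Week 8 (Visit 4) | yes | no | yes |
| Week 12 (Visit 5) | yes | change and percentage change, FAS and PPS | yes |

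Protocol 5.1 puts safety analysis on the SS. The FAS requires that eligibility criteria were met and the SS does not. A randomised but ineligible subject with a safety assessment can therefore be in the SS and outside the FAS.

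**2. How many subjects might be affected**

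The plan states no figure on this point, so there is none to reproduce. The only figure for possible loss is the pilot's completion rate of 72.5% (Protocol 3.5, SAP 3.3). At that rate 200 × (1 − 0.725) = 55 subjects would have no change value, leaving 145. At assumed losses of 5%, 10% and 20% the numbers would be 10, 20 and 40.

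**3. What the week-8 values could recover**

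Take two occasions with monotone missingness: n1 subjects have Visit 5, n2 have Visit 4, and every completer has Visit 4. In large samples, the variance of the estimated Visit 5 mean falls by the following fraction, relative to using completers only:

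reduction = ρ² × (1 − n1/n2)

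Here ρ is the correlation between change at Visit 4 and change at Visit 5. With 27.5% loss, n1/n2 = 72.5 / (72.5 + 27.5s), where s is the share of non-completers who have a Visit 4 value. The documents give neither ρ nor s; both are assumptions.

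| s | ρ | 1 − n1/n2 | ρ² | Variance reduction | Standard error reduction |
|---|---|---|---|---|---|
| 0.25 | 0.70 | 1 − 72.5/79.375 = 0.0866 | 0.4900 | 4.2% | 1 − √0.958 = 2.1% |
| 0.50 | 0.85 | 1 − 72.5/86.25 = 0.1594 | 0.7225 | 11.5% | 1 − √0.885 = 5.9% |
| 0.75 | 0.90 | 1 − 72.5/93.125 = 0.2215 | 0.8100 | 17.9% | 1 − √0.821 = 9.4% |

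The gain shrinks with the loss. At an assumed 10% loss with s = 0.5 and ρ = 0.85, it is 0.7225 × (1 − 90/95) = 3.8% in variance.

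**4. Which visit carries the information**

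The GA-guided adjustment is first made at Visit 3B, the visit at which Group A's week-4 weight is taken. Week-4 values therefore precede any GA-guided change. A subject lost after week 4 adds only pre-adjustment data, so the gain comes mainly from week 8. The formula accordingly counts only Visit 4.

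**The case against.** The strongest defence is that Visit 5 is a legitimate, prespecified time point. Protocol 3.4.2.6 names changes in weight, waist and BMI without interim time points, SAP 4.1.2 fixes Visit 5, and Protocol 5.6 plans two-sample tests. The sentence in 7.5.6 is true as far as Visit 5 goes and does not itself promise by-visit coverage elsewhere. The no-imputation rule applies equally to HbA1c change, HOMA-β and HOMA-IR. On this view the slip justifies a by-visit table, and the choice of model is a matter of preference. Much of this stands: the Visit 5 endpoint should stay, and the planned test is not an error. A model that uses the week-8 values for the same Visit 5 contrast is still better, at little cost.

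Some stronger readings are tempting, but the documents do not support them:

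- *The interim data are discarded.* They remain in the by-subject listing; what is missing is a summary or analysis.
- *Subjects without Visit 5 leave the analysis set.* They drop out of these change comparisons only. The FAS definition does not require Visit 5. Even this is inferred from SAP 7.2.1 and 7.4.2 and is not stated outright.
- *The weight results are biased.* Nothing in the documents links withdrawal to weight. The calculation above concerns precision and does not measure bias.
- *This trial will lose 27.5%.* That rate comes from a single-centre pilot of 40 subjects.

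There are also limits on what could be checked. SAP 7.2.3 (special data notes) is not visible, the table shells are a separate file, and the SAP cites Protocol Version 3.0 while the protocol reviewed here is Version 2.0. The statement that no summary exists applies to the visible text.

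**Conclusion.** The point holds as a modest improvement. The cross-reference in SAP 7.5.6 does not cover weeks 4 and 8, these variables have no safety-set summary, and a subject without Visit 5 contributes nothing to the weight, waist and BMI change comparisons. The likely benefit of using the interim values is a standard error about 2% to 9% smaller, about 6% in the central case. That rests on the assumed correlations, the assumed availability of Visit 4 values and the pilot's loss rate; with lower loss the gain is smaller. Any reduction in bias would depend on dropout being explained by the observed data, which cannot be judged from the documents. The primary endpoint is not touched.

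**What to change.** **SAP 7.5.6.** Replace the sentence with descriptive statistics for weight, waist and BMI by arm, on the SS, at weeks 4, 8 and 12. Give the observed value and the change from screening, with BMI derived from screening height.

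**SAP 7.4.2.** Analyse the absolute change in weight, waist and BMI with a mixed model for repeated measures over the scheduled visits. Include arm, visit, arm-by-visit interaction, centre and screening value, and take the Visit 5 contrast as the endpoint. Keep the planned percentage-change summary and the two-sample test as supportive, so that what SAP 7.7 added is not lost.

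**Cost.** Some SAP wording, one table and one standard model; no new data. The model relies on a missing-at-random assumption, which should be stated, and it pools Visits 3A and 3B as a single week-4 visit, although Group A may be measured up to five days after its Visit 3A. A subject with no follow-up weight still contributes nothing.
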